1.0 Clinical Investigation Plan Overview

This clinical investigation is designed as a prospective, non-randomized study enrolling 73 patients (67 patients for hypothesis testing) to receive the Zenith® Dissection Endovascular System at up to 30 global clinical sites with a maximum enrollment of up to 14 patients per individual site. The primary safety and effectiveness endpoints, as described in Section 3.1, will be compared to the performance goals derived from the combined physician-sponsored studies reported by the Society for Vascular Surgery Outcomes Committee.¹

Any patient with an acute, complicated, type B aortic dissection with either aortic rupture or branch vessel obstruction/compromise that results in malperfusion (see Appendix C, Definitions) is eligible for enrollment in the study. The study flow diagram is presented in Figure 1.

[figure not shown]

Figure 1. Study flow diagram

2.0 Summary of Preliminary Investigations

2.1 Preclinical Testing

Non-clinical tests were conducted in accordance with Good Laboratory Practice requirements, or performed in compliance with verified methods and Standard Operating Procedures to maintain the integrity of the results. *In vitro* testing has established reasonable safety of the device for the expected duration of the study and in the trial population to be studied. Please refer to the Clinical Investigator Brochure for a summary of non-clinical testing.

2.2 Previous Clinical Experience

Refer to the Clinical Investigator Brochure for a complete description of the previous clinical experience with similar devices.

2.3 Justification for the Investigation

This study design and the performance goal are justified given there are no other treatment alternatives that are being commonly practiced at present for patients with acute, complicated Type B aortic dissection. Open surgical repair is rarely performed in these patients due to the very high rate of mortality associated with the procedure. Likewise, medical therapy is not practical as the definitive treatment for these patients, who often require a more aggressive therapy in the form of endovascular/surgical intervention to relieve symptoms and prevent any further adverse clinical sequelae.

3.0 Objectives of the Clinical Investigation

3.1 Primary Objectives

The objective of the study is to evaluate the safety and effectiveness of the Zenith® Dissection Endovascular System in the treatment of patients with complicated, type B aortic dissection. The primary safety endpoint will be rate of freedom from major adverse events (see Appendix C, Definitions) at 30 days. The primary effectiveness endpoint will be the survival rate at 30 days.

3.2 Secondary Objectives

Information redacted

3.3 Specific Hypothesis to be Accepted or Rejected by Statistical Data

3.3.1 Primary Safety Hypothesis

The primary safety endpoint is the rate of freedom from 30-day major adverse events (see Appendix C, Definitions). The published rate of freedom from 30-day MAE from the combined physician-sponsored studies is 61.2%.¹ With a clinically relevant non-inferiority margin of 10%, a performance goal of 51.2% has been established for the primary safety endpoint. The performance goal will be said to have been met provided that the null hypothesis is rejected in favor of the alternative with a one-tailed exact binomial test at the 0.025 level. Given that $\pi_{\text{noMAE}(30)}$ is the probability that a randomly selected patient did not experience any MAE at 30 days, the null and alternative hypotheses are as follows.

Null Hypothesis: The rate of freedom from 30-day MAE, $\pi_{\text{noMAE}(30)}$, does not meet the performance goal (51.2%).

$$H_0: \pi_{\text{noMAE}(30)} \leq 51.2\%$$

Alternate Hypothesis: The rate of freedom from 30-day MAE, $\pi_{\text{noMAE}(30)}$, meets the performance goal (51.2%).

$$H_a: \pi_{\text{noMAE}(30)} > 51.2\%$$

3.3.2 Primary Effectiveness Hypothesis

The primary effectiveness endpoint is the survival rate at 30 days. The published survival rate at 30 days from the combined physician-sponsored studies is 89.4%.¹ With a clinically relevant non-inferiority margin of 10%, a performance goal of 79.4% has been established for the primary effectiveness endpoint. The performance goal will be said to have been met provided that the null hypothesis is rejected in favor of the alternative with a one-tailed exact binomial test at the 0.025 level. Given that $\pi_{s(30)}$ is the probability that

a randomly selected patient is alive at 30 days, the null and alternative hypotheses are as follows.

Null Hypothesis: The survival rate at 30 days, $\pi_{s(30)}$, does not meet the performance goal (79.4%).

$$H_0: \pi_{s(30)} \leq 79.4\%$$

Alternate Hypothesis: The survival rate at 30 days, $\pi_{s(30)}$, meets the performance goal (79.4%).

$$H_a: \pi_{s(30)} > 79.4\%$$

For each endpoint, the hypothesis will be assessed by a one-sided exact binomial test, at a type I error rate of 0.025 and a power of 0.8. The safety and effectiveness of the device will be established if both null hypotheses are rejected in favor of the alternatives at the above mentioned error rates.

4.0 Product Description and Intended Use

The Zenith® Dissection Endovascular System is a disease-specific family of components intended for the treatment of patients with Type B aortic dissection.

4.1 General Product Description

As depicted in Figure 2, the system is comprised of a covered proximal component (Zenith® TX2® Dissection Endovascular Graft) and an uncovered distal component (Zenith® Dissection Endovascular Stent).

[figure not shown]

Figure 2. Zenith® Dissection Endovascular System

Zenith® TX2® Dissection Endovascular Graft

The Zenith® TX2® Dissection Endovascular Graft is predicated on the Zenith® TX2® TAA Endovascular Graft, which is commercially-available in the United States for the treatment of patients with descending thoracic aortic aneurysms and ulcers, and in many countries outside the U.S. for the treatment of patients with aneurysms, dissections, or contained ruptures. The design of the Zenith® TX2® Dissection Endovascular Graft is identical to the Zenith® TX2® TAA Endovascular Graft, except for the removal of fixation barbs in order to provide a disease-specific covered component (Figure 3).

[figure not shown]

Figure 3. Zenith® TX2® Dissection Endovascular Graft

As shown in Table 1, the Zenith® TX2® Dissection Endovascular Graft is available in multiple sizes ranging from 22 to 42 mm in diameter and 79 to 218 mm in length and is also available in both straight and tapered configurations. Tapered components with diameter changes of 4 mm or 8 mm are available.

Table 1. Zenith® TX2® Dissection Endovascular Graft sizes

Graft Diameter (mm)	Length of Straight Component (mm)	Length of Tapered Component – 4 mm Taper (mm)	Length of Tapered Component – 8 mm Taper (mm)
22	79 / 117	n/a	n/a
24	79 / 117	n/a	n/a
26	79 / 136	n/a	n/a
28	82 / 142 / 202	n/a	n/a
30	82 / 142 / 202	n/a	n/a
32	82 / 142 / 202	162 / 202	158 / 196
34	79 / 154 / 204	159 / 199	156 / 194
36	79 / 154 / 204	159 / 199	159 / 199
38	79 / 154 / 204	154 / 204	159 / 199
40	83 / 164 / 218	160 / 210	165 / 205
42	83 / 164 / 218	160 / 210	160 / 210

Zenith® Dissection Endovascular Stent

The Zenith® Dissection Endovascular Stent consists of multiple z-stent segments, made of nitinol, sewn together end-to-end with polyester sutures (Figure 4).

[figure not shown]

Figure 4. Zenith® Dissection Endovascular Stent

As shown in Table 2, the Zenith® Dissection Endovascular Stent is available in multiple sizes.

Table 2. Zenith® Dissection Endovascular Stent sizes

Stent Diameter (mm)	Stent Length (mm)
36	80 / 120 / 180
46	80 / 120 / 185

4.2 Intended Use

The Zenith® Dissection Endovascular System is intended for the endovascular treatment of patients with symptomatic aortic dissection of the descending thoracic aorta having morphology suitable for endovascular repair. Refer to the Instructions for Use (IFU) for further details.

4.3 Product Identification and Tracking

Products under investigation will have a unique lot number and will be tracked throughout the course of the study through use of a Product Log, upon which lot numbers, quantity and disposition of product will be recorded. Product Logs will be maintained in the site's Investigator File. Additionally, the quantity(s), size(s) and lot number of products used in subjects will be recorded on the case report forms.

4.4 Instructions for Use

Please reference the manufacturer's Instructions for Use for complete instructions including installation, storage and handling requirements, preparation for use and precautions to be taken after use.

4.5 Summary of Necessary Training and Experience

Please reference the manufacturer's Instructions for Use for a summary of the necessary training and experience required for use of this product.

4.6 Description of the Necessary Medical or Surgical Procedures

Please reference the manufacturer's Instructions for Use for a description of the procedures involved in the use of this product.

4.7 Adjunctive Devices

At physician discretion, adjunctive devices may be used on an individual basis during either the initial implant procedure or secondary intervention and may include the following (as discussed in Section 6, Methods): aneurysm stent-graft components (for coverage of reentry tears), coils/occluders (for embolization of sources for false lumen flow), uncovered balloon-expandable or self-expanding stents (for branch vessel obstruction), and covered balloon-expandable or self-expanding stents (for coverage of reentry tears involving branch vessels). If adjunctive devices are used, it is recommended that the Instructions for Use (IFU) of that device be reviewed, and the risks of using that device be considered. The specific type/make/model of any adjunctive device implanted during either the initial implant procedure or secondary intervention should be recorded on the case report forms. Additionally, the performance of any adjunctive device placed should be monitored during follow-up.

5.0 Design of the Clinical Investigation

5.1 Type of Investigation

The current investigation is a prospective, non-randomized, non-blinded study.

5.2 Endpoints

The primary safety endpoint will be rate of freedom from major adverse events (see Appendix C, Definitions) at 30 days. The primary effectiveness endpoint will be the survival rate at 30 days. Mortality is the greatest procedural risk associated with alternative treatments and is also the principal outcome any treatment is intended to prevent (up to 50% of patients are at risk for mortality within 48 hours if untreated²).

5.3 Variables to be Measured to Demonstrate Achievement of Endpoints

To evaluate deployment characteristics, procedural outcome and follow-up, the following data points will be collected:

- 1) Assessment of system performance including: deployment issues, ease of insertion, visualization, and ease of removal;
- 2) Clinical utility measures such as days to discharge from hospital;
- 3) Ancillary equipment needed;
- 4) Adjunctive maneuvers including: balloon dilation of iliac arteries, additional stents required, and additional surgical procedures;
- 5) Complications including major adverse events during procedure and at follow-up;
- 6) Device integrity findings at completion of procedure and follow-up: device patency, stent fracture, and graft kinks;
- 7) Type and sources of entry-flow at procedure and follow-up;
- 8) Dimensions of the true and false lumen over the course of follow-up; and
- 9) Secondary interventions performed.

5.4 Measures to be Taken to Avoid or Minimize Bias

This study is not randomized or blinded. It is intended to prospectively collect information regarding the safety and effectiveness of the Zenith® Dissection Endovascular System. The study will utilize uniform definitions for study endpoints, event adjudication by an independent clinical events committee, and imaging data analysis by a centralized core laboratory. Study results will be analyzed in accordance with a prospectively defined analysis plan.

5.5 Study Criteria

Assessment of entry criteria will be based upon data available pre-operatively. Data obtained peri-operatively and post-operatively (including the results from core lab analysis of pre-procedure imaging) may contradict pre-operative assessment. However, such contradiction is not considered a violation of the Clinical Investigation Plan and should not be construed as evidence of inadequate or inaccurate pre-operative assessment with respect to the enrollment criteria or evidence of inappropriate enrollment. Enrollment is to be based upon best available pre-operative data. Some criteria relate to subjective assessment while other criteria are considered absolute and able to be

determined definitively. Variability in assessment between centers, investigators, and observers is expected with several criteria.

5.5.1 Inclusion Criteria

A patient is deemed suitable for inclusion in the study if the patient has an acute, complicated, Type B aortic dissection with at least one of the following characteristics (see Appendix C, Definitions):

- 1) Aortic rupture; or
- 2) Branch vessel obstruction/compromise resulting in malperfusion

5.5.2 Exclusion Criteria

Patients must be excluded from the study if any of the following conditions are true:

General Exclusion Criteria

- 1) Age < 18 years;
- 2) Other medical condition (e.g., cancer, congestive heart failure) that may cause the patient to be non-compliant with the Clinical Investigation Plan, confound the results, or is associated with limited life expectancy (i.e., less than 2 years);
- 3) Pregnant, breast-feeding, or planning on becoming pregnant within 60 months;
- 4) Unwilling or unable to comply with the follow-up schedule;
- 5) Inability or refusal to give informed consent; or
- 6) Simultaneously participating in another investigative device or drug study. (The patient must have completed the primary endpoint of any previous study at least 30 days prior to enrollment in this study.)

Medical Exclusion Criteria

- 7) Suspicion of bowel necrosis (as determined by the implanting physician based on imaging observations, peritoneal signs, surgical exploration, elevated serum lactate levels, and/or acidosis)
- 8) ASA risk class V (i.e., moribund patient not expected to live 24 hours with or without operation)
- 9) Embolic stroke within the last 14 days prior to potential enrollment in the study or

- hemorrhagic stroke within 30 days prior to potential enrollment in the study;
- 10) Diagnosed or suspected congenital degenerative connective tissue disease (e.g., no Marfan's or Ehler-Danlos syndrome);
 - 11) Systemic infection (e.g., sepsis);
 - 12) Bleeding diathesis, uncorrectable coagulopathy, or refuses blood transfusion;
 - 13) Allergy to stainless steel, polyester, solder (tin, silver), polypropylene, nitinol, or gold;
 - 14) Untreatable reaction to contrast, which, in the opinion of the investigator, cannot be adequately pre-medicated;
 - 15) Surgical or endovascular AAA repair within 30 days before or after dissection repair;
 - 16) Previous placement of a thoracic endovascular graft;
 - 17) Prior open repair involving descending thoracic aorta including suprarenal aorta and/or arch; or
 - 18) Interventional and/or open surgical procedures (unrelated to dissection) within 30 days before or after dissection repair.

Anatomical Exclusion Criteria

- 19) Dissection of aorta proximal to left subclavian artery (either primary entry tear or most proximal extent of dissection);
- 20) Proximal landing zone length measuring < 20 mm between the left common carotid artery and most proximal extent of dissection (covering left subclavian artery is acceptable, except in patients with a dominant vertebral artery off of the arch in the region of the subclavian or a dominant vertebral off of the subclavian);
- 21) Proximal landing zone diameter for proximal stent-graft component < 20 mm or > 38 mm, measured outer-wall to outer-wall on a sectional image or multiplanar reconstruction;
- 22) Aortic arch radius of curvature < 35 mm (if device deployed in the arch);
- 23) Distal landing zone diameter for proximal stent-graft component < 20 mm (estimate based on transaortic diameter) or > 38 mm (estimate based on true lumen diameter), measured outer-wall to outer-wall on a sectional image or multiplanar reconstruction;
- 24) Diameter < 20 mm (estimate based on transaortic diameter) or > 38 mm (estimate based on true lumen diameter) for any segment of vessel into which deployment of bare stent device is intended, measured outer-wall to outer-wall on a sectional image or multiplanar reconstruction;
- 25) Prohibitive angulation in segments of vessel into which deployment of bare stent

- device is intended (e.g., radius of curvature < 35 mm, or localized angle > 45 degrees);
- 26) Both iliac arteries having prohibitive tortuosity, calcification, occlusive disease or arterial diameter, measured inner-wall to inner-wall on a sectional image, that are not conducive to placement of the introducer sheath (use of access conduit permitted);
 - 27) Prohibitive calcification, occlusive disease, or angulation in intended proximal landing zone;
 - 28) Circumferential thrombus in region of intended proximal landing zone;
 - 29) Inability to preserve the native left common carotid artery and celiac artery origins; or
 - 30) Aneurysm or angulation in the distal thoracic aorta that would preclude advancement of the introduction system.

5.6 Point of Enrollment

Point of enrollment will be based on the intent-to-treat population, and is defined to include any patient for whom the treatment procedure is initiated. More specifically, once a procedure has begun (i.e., cutdown or percutaneous access initiated), the patient would be included in the intent-to-treat population. The patient's informed consent will be obtained and assessment of the patient's conformance to the inclusion/exclusion criteria will occur prior to the procedure.

Study results will also be analyzed with respect to the consented patient population (i.e., all patients who gave consent to participate in the study, regardless of treatment).

5.7 Enrollment Objective

67 patients will be enrolled in accordance with Version 4 of the CIP at up to 30 global clinical sites with a maximum enrollment of up to 14 patients per individual site. In order to account for patients who would not be eligible for enrollment based on the clarifications reflected in Version 4 of the CIP, the total enrollment for the study has increased to provide for six additional patients (73 patients total).

6.0 Methods

6.1 Subject Consent

Patients who meet the inclusion/exclusion criteria will be invited to participate in this investigation. All patients eligible for entry into the investigation will have the Clinical Investigation Plan explained to them, as well as potential risks and benefits of their participation in the investigation. Each patient who agrees to participate will be required to sign an informed consent document prior to the procedure.

6.2 Pre-procedure

Stent-grafts and dissection stents are sized based on the findings from pre-operative computerized tomography (CT) in conjunction, if necessary, with other imaging modalities such as angiograms and intravascular ultrasound (IVUS). Refer to the Instructions for Use for details regarding the suggested sizing guidelines.

6.3 Procedure

Standard techniques for placement of arterial access sheaths, guiding catheters, angiographic catheters, and wire guides should be employed during use of the Zenith® Dissection Endovascular System. Care must be exercised in placing of sheaths and wireguides, and in advancing the delivery system of the devices. Molding balloon angioplasty in the dissected region of the aorta must be avoided.

Precautions should be taken to minimize the risk of stroke. All air should be flushed from sheaths and lumens before insertion using elevated tip technique. Wire placement and manipulation in the ascending thoracic aorta and aortic arch should be minimized.

Fluoroscopic guidance and angiography should be used throughout the procedure to verify positioning of the device with respect to the patient's anatomy.

Refer to institutional protocols relating to anesthesia, anticoagulation, access technique, spinal drainage and monitoring of vital signs. Coverage of the left subclavian artery is acceptable; however, revascularization of the left subclavian artery should be considered.³

Refer to the Instructions for Use for complete details regarding use of the Zenith® Dissection Endovascular System. In general, placement of a bare stent following

coverage of the primary tear with a stent-graft is recommended to support the distal, delaminated segments of the aorta. However, bare stent placement following stent-graft coverage of the primary entry tear may not be necessary in patients for whom all of the following are applicable:

- No continued signs or symptoms of obstructed/compromised branch vessel (if patient was included in the study for obstructed/compromised branch vessel) after placement of the proximal component
- Systolic pressure gradient ≤ 20 mm Hg between the aortic root and a distal obstructed aortic segment/vessel (if patient was included in the study for obstructed/compromised branch vessel)
- No false lumen flow through secondary re-entry tears

Bare stent deployment within regions of tortuosity or acute angulation should be avoided. It might be necessary to use multiple Zenith® Dissection Endovascular Stents of shorter length, so as to avoid deployment of the bare stents within tortuous or acutely angled segments.

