6.5 Post-operative Treatment of Entry-flow

All instances of entry-flow should be evaluated promptly with an angiogram, and if necessary a selective angiogram, to determine the origin of the flow. The completion angiogram should be examined carefully for entry-flow.

Type I entry-flow should be promptly considered for treatment using additional balloon seating or if necessary, placement of additional stent-graft prostheses (use of Zenith main body extensions is recommended). Placement of embolization coils may be needed to occlude sources of Type II entry-flow and collateral flow if the leak is believed to be significant and/or in the presence of an enlarging false lumen. Use of occluder devices (e.g., Amplatzer) to embolize the left subclavian artery has also been reported. Type III entry-flow represents graft or junctional defects and should be promptly considered for treatment with additional ballooning or prostheses. Type IV entry-flow is generally

associated with grafts with a high porosity and is unlikely with the graft component of this system. Secondary/reentry tears may also require coverage with placement of additional stent-graft prostheses in the aorta or covered balloon-expandable and/or self-expanding stents in branch vessels if flow through the tear is significant and/or in the presence of an enlarging false lumen.

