APPENDIX C
Definitions

Calcification: Landing zone and iliac calcification will be graded based upon the following:

None:	Lack of calcification;
Mild:	Less than 40% circumferential calcification;
Moderate:	40-70% circumferential calcification; or
Severe:	Greater than 70% circumferential.

Clinical Utility Measures: Number of blood transfusions; Ventilator days; Days to resumption of oral fluids; Days to resumption of normal diet; Days to resumption of normal bowel function; Duration of ICU stay; Days to discharge.

Disabling Chronic Obstructive Pulmonary Disease: Forced expiratory volume (FEV₁) < 1.0 liter or receiving home oxygen therapy.

Dissection Grade:

Acute:	Within 14 days of onset;
Subacute:	Between 15 days and 30 days of onset; or
Chronic:	Between 31 days and 90 days of onset.

Embolization: Clinical evidence of ischemic tissue remote from the operative field, caused by air, thrombus dislodged from the aneurysmal sac, aortic neck, and/or false lumen, including those tissues supplied by vessels in the head, renal arteries, aortic visceral branches, pelvic vessels, and vessels of the upper and lower limbs. This is, of course, distinct from pre-operative, operative or post-operative intentional embolization procedures (e.g., to treat Type II entry-flow).

Entry-flow: Contrast-enhanced blood entering the false lumen for one or more of the following reasons:

Type I entry-flow: Entry-flow caused by peri-prosthetic flow at the proximal and/or distal seal zones;

Type II entry-flow: Entry-flow caused by retrograde flow from patent collateral vessels into the false lumen through the primary tear;

Collateral entry-flow: Entry-flow caused by retrograde flow from collateral vessels directly into the false lumen;

Type III entry-flow: Entry-flow caused by a defect in the graft fabric, inadequate seal (between covered graft components only), or disconnection of covered graft ancillary components;

Type IV entry-flow: Entry- flow caused by graft fabric porosity, often resulting in a generalized blush of contrast within the false lumen; or

Unknown entry-flow: Entry-flow through undefined origin.

Left Ventricular Ejection Fraction: The measurement of the left ventricular function in the resting state. The normal LVEF ranges between 55% and 80% (mean = 67%).

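### Section 6.3 bars molding balloon angioplasty in dissected aorta, while Section 6.5 recommends considering ballooning for Type I and Type III entry-flow with no limit on location; the two need reconciling for distal Type I and some Type III flow

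*Combined protocol and SAP*

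**What the plan says.** Section 6.3 (Procedure) contains a precaution in mandatory terms: "Molding balloon angioplasty in the dissected region of the aorta must be avoided". It is limited by location, to the dissected aorta, and by nothing else.

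Section 6.5 (Post-operative Treatment of Entry-flow) deals with leaks into the false lumen. Despite its title it reaches into the procedure: "The completion angiogram should be examined carefully for entry-flow". On treatment it says:

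- Type I: "Type I entry-flow should be promptly considered for treatment using additional balloon seating or if necessary, placement of additional stent-graft prostheses".
- Type III: "Type III entry-flow represents graft or junctional defects and should be promptly considered for treatment with additional ballooning or prostheses".

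Neither sentence names a location, and Section 6.5 does not mention the precaution in 6.3.

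Appendix C defines entry-flow in general as "Contrast-enhanced blood entering the false lumen for one or more of the following reasons". Type I is "Entry-flow caused by peri-prosthetic flow at the proximal and/or distal seal zones". Type III is a defect in the graft fabric, "inadequate seal (between covered graft components only), or disconnection of covered graft ancillary components".

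**The concern.** An operator who sees a leak on the completion angiogram is still in the procedure governed by 6.3 and is also told by 6.5 what to consider. If the leak lies where the aorta is dissected, one section rules out a balloon maneuver and the other puts ballooning among the options, first in order for Type I. The protocol does not say which section prevails, or whether the two describe different maneuvers.

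Two things are at stake. The first is patient safety: following 6.5 as written could breach a precaution that 6.3 treats as mandatory. The second is uniformity: up to 30 sites may take part, and reasonable operators could resolve the question differently.

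**Working it through.** The plan gives no figure on this point and no arithmetic applies. The check is whether both sections can govern the same segment of aorta at the same time.

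**Timing.** Section 6.3 governs the implant procedure. Section 6.5 includes the completion angiogram. The two overlap.

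**Strength of wording.** Section 6.3 is a prohibition without exception. Section 6.5 is a recommendation to consider treatment promptly. For Type I it names balloon seating first and a further stent-graft if needed; for Type III it offers ballooning or prostheses as alternatives.

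**Location, taken by type of flow:**

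| Entry-flow | What fixes the location | Can it lie in dissected aorta? | 6.3 against 6.5 |
|---|---|---|---|
| Type I, proximal | Exclusion criterion 20 rules out patients with less than 20 mm between the left common carotid artery and the upper end of the dissection | No, if the graft lands in that zone | Compatible |
| Type I, distal | Appendix C includes the distal seal zone; exclusion criterion 23 sets the stent-graft's distal landing zone limits at under 20 mm on the transaortic diameter and over 38 mm on the true lumen diameter | Yes: a true-lumen measurement has meaning only if the zone may be dissected | Not reconciled |
| Type III | Appendix C gives the mechanism (fabric, seal between covered components, disconnection) and no aortic location | Sometimes, by inference: the graft covers the primary tear, so a defect or junction may lie alongside dissected aorta | Not reconciled where it does |

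Section 6.3 supports the distal reading: it describes the aorta that the bare stent is meant to support, beyond the stent-graft, as delaminated.

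**Terms.** Section 6.3 speaks of molding balloon angioplasty, 6.5 of balloon seating for Type I and plain ballooning for Type III. Appendix C defines none of the three, and no section distinguishes them.

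**Result.** The sections agree for proximal Type I flow. They are unreconciled for distal Type I flow, and for Type III flow where the defect lies in dissected aorta.

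**The case against.** The strongest reply is that an operator can obey both sections. Section 6.3 says where a balloon may not be used; 6.5 lists options to consider and names prostheses for both types. Read together, 6.3 simply limits 6.5. This reading is possible, and it is why the passages should not be called flatly contradictory. But the plan does not state it. Under it, the balloon step that 6.5 lists first for Type I would not apply to a distal leak in dissected aorta, and 6.5 gives no sign of that.

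A second reply is that seating a graft is a different act from molding dissected aorta. That may be so in practice, but the plan never draws the distinction, and the word used for Type III is simply ballooning.

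A third reply is that 6.3 refers to the Instructions for Use for complete details, and these may settle the matter. They are not among the documents, so this can be neither confirmed nor excluded. Even if they do, the protocol's own sections should agree with them and with each other.

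Three stronger readings are tempting and are not supported:

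- That 6.5 directs ballooning. It asks only that treatment be considered.
- That the definitions alone place these leaks in dissected aorta. Appendix C is silent on that; distal Type I needs criterion 23 as well, and Type III rests on inference.
- That any resulting harm would count in both primary endpoints. The list of major adverse events in Appendix C includes neither death nor aortic rupture. An aortic injury would reach the safety endpoint only through a listed event, and the 30-day survival endpoint only through death.

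**Conclusion.** The point holds as an unresolved inconsistency in procedural guidance, confined to distal Type I entry-flow and to Type III entry-flow where the defect lies in dissected aorta. It rests on two assumptions: that the true-lumen limit in criterion 23 means the distal landing zone may be dissected, and that the three balloon terms are not meant to differ in a way the protocol leaves unsaid. If the sponsor intends such a difference, the remedy is still to state it.

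Its size cannot be given. The documents report no frequency for distal Type I or Type III flow and no rate of harm from ballooning. A reader might infer a threat to the trial's statistical conclusions; the documents do not support that. The sample size and both exact binomial tests stand as they are. The case for acting is patient safety and consistent conduct across sites, and it is strong enough that the change should be made, since the precaution is mandatory in tone and the correction is simple.

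**What to change.** The sponsor's clinical team should reconcile Sections 6.3 and 6.5 and check both against the Instructions for Use. The revised text should:

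- state which instruction applies for each entry-flow type and location (proximal seal zone, distal seal zone, graft fabric or junction);
- say whether seating, ballooning and molding are different maneuvers and, if so, define them in Appendix C;
- add a cross-reference between 6.3 and 6.5. Section 6.6 already relies on 6.5 for follow-up treatment, so it should be read again once 6.5 is settled.

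The content of the rule is a clinical decision, and no view is taken here on which instruction is right.

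The cost is a wording change and a notification to sites. No procedure, visit, data item or analysis is added.
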